7 TREATMENTS

7.1 Subject Assignment

After informed consent documents are signed, patients who meet all eligibility criteria will begin study treatment.

7.2 Method of Assignment to Treatment

This is an open-label trial and each subject will sequentially receive supplemental oxygenation followed by sequential periods of both investigational treatment (nasal reservoir cannula plus nasal cannula) and standard of care treatment (supplemental oxygenation through nasal cannula alone). Patients will be randomized so that the order of initial treatment (nasal reservoir cannula plus nasal cannula vs. nasal cannula) is balanced between subjects. Patients with a body weight of 8-13 kg will receive treatment with a small 30 ml mask and patients with a body weight of 14-26 kg will receive treatment with a large 50 ml mask. All subjects will receive standard of care for their underlying disease according to WHO recommendations, including availability of standardized care of oxygen therapy.

8 ADVERSE EVENT REPORTING

8.1 Definition of Adverse Event

For purposes of this trial, an adverse event (AE) will be defined as **any** new unfavorable or unintended sign, symptom, or disease or change of an existing condition, which occurs during or after treatment, whether or not considered treatment-related. If clinically significant laboratory values lead to or are associated with clinical symptom(s), the diagnosis should be reported as an AE. Lack of treatment effect is not an adverse event in clinical trials because the purpose of the clinical trial is to establish (or evaluate for) a treatment effect.

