- Baseline (pre-treatment): Once eligibility criteria are met, physical examination, including vital signs and capillary refill time; blood glucose (point of care); malaria rapid diagnostic test; and concomitant medication information will be obtained. In addition, a metabolic panel will be recorded *only* if obtained as standard of care. Any baseline assessment obtained during the screening period will be used as the baseline value. Patients will be placed on supplemental oxygen consistent with standard of care. Based on the body weight of the patients the size (small or large) of the nasal reservoir cannula to be used during the intervention periods will be determined.
- Period 1 (Group A: nasal reservoir cannula plus nasal cannula for 1 hr, Group B: standard nasal cannula alone) will include:

Period 1 (1 hr):

- Continuous monitoring of transdermal end-tidal carbon dioxide (CO₂) with recording every 15 min.
- Continuous monitoring of SpO₂ by pulse oximetry with recording every 15 min.
- Record vital signs every 15 min.
- Record oxygen flow (L/min) every 15 min.
- Record concomitant medication information.
- Record adverse events.

End of Period 1:

- Physical examination, including capillary refill time; capillary blood gases (P_aO₂, P_aCO₂, pH, base excess, lactate); and SICK score.
- Period 2 (Group A: nasal cannula for 1 hr, Group B: nasal reservoir cannula with standard nasal cannula alone) will include:

Period 2 (1 hr):

- Continuous monitoring of transdermal end-tidal carbon dioxide (CO₂) with recording every 15 min.
- Continuous monitoring of SpO₂ by pulse oximetry with recording every 15 min.
- Record vital signs every 15 min.

- Record oxygen flow (L/min) every 15 min.
- Record concomitant medication information.
- Record adverse events.

End of Period 2:

- Physical examination, including capillary refill time; capillary blood gases (P_aO₂, P_aCO₂, pH, base excess, lactate); and SICK score.
- Study duration is from the beginning of Period 1 to end of Period 2 (approximately 2 hour).

Sample Size and Number of Sites:

• The target sample size for the study (up to 20 patients) is consistent with feasibility studies for other clinical interventions. Planned number of sites: 1 (Department of Pediatrics, Makerere University, Kampala, Uganda).

Removal of Subjects from Investigational Study Treatment or Assessment:

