4.2.1.1 Screening Evaluations

The following screening assessments must be done to determine eligibility for study participation. Written consent from parents(s)/guardian(s) will be obtained before conducting any study procedures.

- Screen for age and weight entry criteria (see Section 5).
- Medical history.
- Physical examination including body weight.
- Severe pneumonia (based on WHO criteria).
- Peripheral blood oxygen saturation (SpO₂) by pulse oximetry on air.
- Capillary blood gas with lactate (P_aO₂, P_aCO₂, pH, base excess, lactate) to evaluate for acidosis and hypercapnia.
- Completion of SICK score form (based on physical exam and SpO₂) data.
- Rapid hemoglobin and complete blood count (CBC).

- Malaria rapid diagnostic test.
- Point of care blood glucose.
- Comprehensive metabolic panel will be obtained *only* if indicated as part of standard care.

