8.1.1 Reporting Procedures for All Adverse Events

The investigator remains responsible for following, through an appropriate health care option, AEs that are serious or that caused the subject to discontinue the study. The subject should be followed until the event is resolved or explained. Frequency of follow-up is left to the discretion of the investigator.

Adverse event information will be collected through the study period. The investigator is responsible for assessing and recording all AEs. Each AE will be recorded and classified for intensity, seriousness, and causality. All AEs either observed by the investigator or reported by the subject will be recorded regardless of causality. The investigator will follow the subject until an AE resolves or stabilizes.

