8.1.2 Adverse Event Relationship to Study Treatment or Procedure

The relationship of an AE to the study treatment or procedure should be based on the judgment of the investigator and assessed using the following the guidelines:

- Definitely: Previously known toxicity of study treatment or procedure; or an event that follows a reasonable temporal sequence from administration of the study treatment or procedure; that follows a known or expected response pattern to the suspected study treatment or procedure; that is confirmed by stopping or reducing the dosage of the study treatment or procedure; and that is not explained by any other reasonable hypothesis.
- Probably: An event that follows a reasonable temporal sequence from administration of the study treatment or procedure; that follows a known or expected response pattern to the suspected study treatment or procedure; that is confirmed by stopping or reducing the dosage of the study treatment or procedure; and that is unlikely to be explained by the known characteristics of the subject's clinical state or by other interventions.
- Possibly: An event that follows a reasonable temporal sequence from administration of the study treatment or procedure; that follows a known or expected response pattern to

that suspected of study treatment or procedure; but that could readily have been produced by a number of other factors.

 Unrelated: An event that can be determined with certainty to have no relationship to the study treatment or procedure.

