10.5.6 Safety Analyses

Treatment-emergent AEs are defined as AEs occurring after the first initiation of treatment until completion of treatment. Duration of treatment will be summarized by treatment group. The incidence of all reported AEs and treatment-related AEs will be tabulated by treatment group. AEs will be classified by system organ class and verbatim term.

AEs will be listed and summarized by treatment group, verbatim term, severity, seriousness, and relationship to study drug. In the event of multiple occurrences of the same AE with the same verbatim term in one subject, the AE will be counted once as the worst occurrence. The incidence of AEs will be tabulated by system organ class and

treatment group. AEs leading to premature discontinuation of study drug or withdrawal from the study will be summarized and listed in the same manner.

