APPENDIX H Data and Safety Monitoring Plan

A. Confidentiality

- 1. Protection of Subject Privacy— During this study, a physical examination and blood tests will be performed. Data will be kept in strict confidence. No information will be given to anyone without permission from the parents of the participant. This statement guarantees confidentiality. Confidentiality is assured by use of study identification numbers. All clinical and laboratory data will be identified only by the study identification number unique to the subject. No participant specimens will be stored for future use.
- 2. Database Protection— The database is secured with password protection. The informatics manager receives only coded information, which is entered into the database under those identification codes. Electronic communication with outside collaborators involves only unidentifiable information.
- 3. Confidentiality during Adverse Event Reporting— Adverse event reports will not include subject-identifiable material. Each will include the study identification number only.

B. Adverse Event Information

1. Definitions- An adverse event (AE) will be defined as **any** new unfavorable or unintended sign, symptom, or disease or change of an existing condition, which occurs during or within 1 hour after treatment, whether or not considered treatment-related. If clinically significant laboratory values lead to or are associated with clinical symptom(s), the diagnosis should be reported as an AE. Lack of treatment effect is not an adverse event in clinical trials because the purpose of the clinical trial is to establish (or evaluate for) a treatment effect.

A serious adverse event (SAE) is defined as an AE that suggests a significant hazard or side effect, regardless of the relationship to study treatment. An SAE includes, but may not be limited to, any event that:

- Results in death.
- Is life-threatening. This definition implies that the subject, in the view of the investigator, is at immediate risk of death from the event. It does not include an event that, had it occurred in a more serious form, might have caused death.
- Requires inpatient hospitalization or prolongs existing hospitalization.
- Results in persistent or significant disability/incapacity.
- 2. Classification of AE Severity AEs will be labeled according to severity, which is based on their impact on the patient, per this Event Grading Scale:

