 - Grade 1 Mild: Transient of mild discomfort; no limitation in activity; no medical intervention/therapy required.
 - Grade 2 Moderate: Mild to moderate limitation in activity some assistance may be needed; no medical intervention/therapy required.

- Grade 3 Severe: Marked limitation in activity, some assistance usually required; medical intervention/therapy required, hospitalizations possible.
- Grade 4 Life-threatening: Extreme limitation in activity, significant medical intervention/therapy required.
- 3. AE Attribution Scale— AEs will be categorized according to the likelihood that they are related to the study intervention. The relationship of an AE/SAE to the study treatment or procedure should be based on the judgment of the investigator and assessed using the following the guidelines:
 - Definitely: Previously known toxicity of study treatment or procedure; or an event that follows a reasonable temporal sequence from administration of the study treatment or procedure; that follows a known or expected response pattern to the suspected study treatment or procedure; that is confirmed by stopping or reducing the dosage of the study treatment or procedure; and that is not explained by any other reasonable hypothesis.
 - Probably: An event that follows a reasonable temporal sequence from administration of the study treatment or procedure; that follows a known or expected response pattern to the suspected study treatment or procedure; that is confirmed by stopping or reducing the dosage of the study treatment or procedure; and that is unlikely to be explained by the known characteristics of the subject's clinical state or by other interventions.
 - Possibly: An event that follows a reasonable temporal sequence from administration of the study treatment or procedure; that follows a known or expected response pattern to that suspected of study treatment or procedure; but that could readily have been produced by a number of other factors.
 - Unrelated: An event that can be determined with certainty to have no relationship to the study treatment or procedure.
- 4. Expected Risks— Expected risks to the subjects are mild discomfort due to blood draws. These risks are considered to be minimal and are addressed in the protocol and consent form. There is minimal risk associated with the device.

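### Adverse event collection opens at treatment, so harm from a screening procedure in a consented child before Period 1 has no written route to be recorded or reported

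*Protocol*

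**What the plan says.** Protocol Section 8.1 defines an adverse event as a new or changed unfavourable finding "which occurs during or after treatment, whether or not considered treatment-related". The Data and Safety Monitoring Plan (Appendix H, B.1) has the same start but closes the window: "which occurs during or within 1 hour after treatment, whether or not considered treatment-related". Section 8.1.1 adds: "Adverse event information will be collected through the study period". The synopsis gives the extent of the study: "Study duration is from the beginning of Period 1 to end of Period 2". In Appendix A the AE row is marked under Period 1 and Period 2 and is blank under Screening and Period 0. Section 8.1.3 defines a serious adverse event as an AE with further features, and asks for reports of those arising in the course of the study.

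On procedures, Section 4.2.1.1 says that parental consent "will be obtained before conducting any study procedures", and then lists the screening work. On attribution, Section 8.1.2 reads: "The relationship of an AE to the study treatment or procedure should be based on the judgment of the investigator". Appendix H B.3 repeats this. Appendix H B.4 names a procedural risk: "Expected risks to the subjects are mild discomfort due to blood draws".

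**The concern.** From consent, a child is exposed to what the study does. The protocol accepts that a study procedure can cause harm, since its attribution scale covers procedures and the expected risk it names is a procedural one. Yet the definition of an AE, the place to record it and the SAE duty all begin later, at treatment.

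The child of most interest is one who is consented, worsens during or after screening, and is then excluded under criterion 11 in Section 6.1 because saturation on oxygen is below 90% just before Period 1. That child never receives study treatment, so no event can fall during or after it. The child is also outside the full analysis population, which Section 10.5.1 restricts to randomised and treated subjects. The study is meant to inform both the safety and the conduct of a larger trial, and harm from its own screening bears on both.

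**Working it through.** No design figure depends on this point, so the check sets the texts side by side and follows typical cases through them. A short count of blood sampling then shows how much of it precedes the window.

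**Where each text opens and closes the window**

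| Place | Opens | Closes |
|---|---|---|
| Section 8.1 | at treatment | not stated |
| Appendix H B.1 | at treatment | 1 hour after treatment |
| Section 10.5.6 (treatment-emergent) | first initiation of treatment | completion of treatment |
| Appendix A, AE row | Period 1 | Period 2 |
| Synopsis, study duration | start of Period 1 | end of Period 2 |

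The opening is the same throughout, provided that treatment means Period 1 onward. The closings differ, but this point does not rest on them.

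**Following an event through the rules**

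1. Harm from a screening procedure that starts and resolves before Period 1: not during or after treatment, so not an AE. Without being an AE it cannot be an SAE. Appendix A has no cell for it.
2. The same harm in a child then excluded under criterion 11: there is no treatment to which the definition can attach, and no place in the full analysis population.
3. Harm from a screening procedure that first appears, or worsens, during Period 1: an AE under Section 8.1.
4. Harm from the capillary gas at the end of Period 1 or Period 2: during or directly after treatment, so an AE under Section 8.1 and Appendix H B.1.

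Only cases 1 and 2 are lost.

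**How much sampling precedes the window (Appendix J)**

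The metabolic panel (3 mL) is left out because it is taken only as standard care.

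- Printed totals without the panel: 1.19 mL at screening and 1.19 + 2 × 0.095 = 1.38 mL overall, as the appendix shows.
- Sum of the listed screening items: 0.095 + 1 + 0.01 + 0.05 + 0.05 = 1.205 mL. Overall: 1.205 + 2 × 0.095 = 1.395 mL. The 0.015 mL difference from the printed figure is trivial.
- Share by volume before Period 1: 1.205 / 1.395 = 86.4%. The printed figures give 1.19 / 1.38 = 86.2%.
- Share by capillary gases before Period 1: 1 of 3.

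The two shares point in different directions. Volume is a poor measure of discomfort, so neither is an estimate of harm missed. They show only that study sampling takes place on both sides of the boundary.

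**The case against.** The strongest reply is that the plan is coherent as written. Every text that fixes a start fixes the same one. The attribution wording does not contradict it: a causality scale says how to classify an event already counted as an AE, and procedures inside the window (end-of-period blood gases, transdermal monitoring, fitting the mask) give the word procedure real content. Opening collection at treatment is a choice, and both device periods are covered. This stands. A reader might infer that the protocol contradicts itself on when the window opens; it does not.

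Four other stronger readings also fail.

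- That harm from study blood draws in general goes uncounted. The draws at the ends of both periods are covered.
- That harm during the oxygen run-in is lost study harm. The run-in is standard of care. Section 7.2 places it before the two periods, Section 4.2.2.1 lists it under the Period 1 heading, and treatment is not defined.
- That reporting is barred. Nothing forbids an investigator from recording an earlier event; what is missing is a rule or a field that leads to it.
- That blood-draw discomfort is the only risk assumed, so that the report after 10 patients would miss most of the relevant exposure. Appendix H also lists hypercapnia, need for ventilation and pneumothorax as potential risks, and that report does not tie its pre-study assumptions to blood draws.

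A child excluded on saturation is also not invisible: that reading is a scheduled baseline assessment, and eligibility is reviewed every two weeks. Neither of these records or reports an adverse event.

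**Conclusion.** The gap is real and narrow. Under the written rules, an event caused by a screening procedure in a consented child, confined to the time before Period 1, is neither an AE nor an SAE and has no scheduled place to be recorded. This is a stated rule, not a detail left to an analysis plan.

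Severity is minor. The device comparison and the treatment-emergent analysis do not change. The number of children affected cannot be worked out: the protocol plans for up to 20 patients but gives no number expected to be consented and then not treated, and no rate of screening harm.

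The conclusion assumes that treatment means Period 1 onward, as Section 7.2, Appendix A and the study duration indicate. It also assumes that at least some of the screening tests are done for the study. Section 5 calls the trial's assessments standard for these patients, so the study-specific share cannot be settled from the protocol.

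**What to change.** - **Section 8.1 and Appendix H B.1:** collect all SAEs, and AEs related to a study procedure, from consent. Collect all other AEs from the start of treatment, as now. State that, for this purpose, treatment begins at Period 1.
- **Appendix A:** add a mark for AE recording under Screening and Period 0.
- **Section 10.5.6:** keep the treatment-emergent definition ("AEs occurring after the first initiation of treatment until completion of treatment") for the device comparison. Add a separate listing of pre-treatment events that includes consented children who were never treated.

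The cost is wording in these places, slightly more recording and one extra listing. No assessment is added and no clinical rule changes.

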8.1.1 Reporting Procedures for All Adverse Events

The investigator remains responsible for following, through an appropriate health care option, AEs that are serious or that caused the subject to discontinue the study. The subject should be followed until the event is resolved or explained. Frequency of follow-up is left to the discretion of the investigator.

Adverse event information will be collected through the study period. The investigator is responsible for assessing and recording all AEs. Each AE will be recorded and classified for intensity, seriousness, and causality. All AEs either observed by the investigator or reported by the subject will be recorded regardless of causality. The investigator will follow the subject until an AE resolves or stabilizes.

8.1.2 Adverse Event Relationship to Study Treatment or Procedure

The relationship of an AE to the study treatment or procedure should be based on the judgment of the investigator and assessed using the following the guidelines:

- Definitely: Previously known toxicity of study treatment or procedure; or an event that follows a reasonable temporal sequence from administration of the study treatment or procedure; that follows a known or expected response pattern to the suspected study treatment or procedure; that is confirmed by stopping or reducing the dosage of the study treatment or procedure; and that is not explained by any other reasonable hypothesis.
- Probably: An event that follows a reasonable temporal sequence from administration of the study treatment or procedure; that follows a known or expected response pattern to the suspected study treatment or procedure; that is confirmed by stopping or reducing the dosage of the study treatment or procedure; and that is unlikely to be explained by the known characteristics of the subject's clinical state or by other interventions.
- Possibly: An event that follows a reasonable temporal sequence from administration of the study treatment or procedure; that follows a known or expected response pattern to

that suspected of study treatment or procedure; but that could readily have been produced by a number of other factors.

 Unrelated: An event that can be determined with certainty to have no relationship to the study treatment or procedure.

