6.2 Removal of Subjects from Investigational Device Treatment or Assessment

6.2.1 Early Discontinuation of Investigational Device Treatment

A subject must prematurely discontinue investigational device (nasal reservoir cannula) treatment under any of the following circumstances:

- The subject's parent(s)/guardian(s) wishes investigational device treatment to be discontinued for any reason.
- The investigator wishes the subject to discontinue investigational device treatment, especially, but not limited to the investigator concluding that further treatment puts the subject at unacceptable risk.
- The subject develops a condition or begins a therapy that would have excluded entry into the study (e.g., hypercapnia, acidosis, hemodynamic instability, requirement of intubation or positive pressure ventilation).

A parent(s)/guardian(s) has the right for the subject to discontinue investigational device treatment at any time for any reason without prejudice to current or future medical care by the investigator or other physician at the institution.

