10.5.3 Subject Disposition

Study subject disposition will be summarized by treatment group. Subjects who discontinued study drug prematurely or withdrew from the study will be summarized and listed, with reason for early termination/withdrawal.

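### Each adverse event gets one causality rating that pools device, cannula and study procedures, so the planned tables give no investigator-attributed, mask-specific related-AE rate

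*Protocol*

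**What the plan says.** **Rating.** Section 8.1.2: "The relationship of an AE to the study treatment or procedure should be based on the judgment of the investigator". Each of its four levels names treatment and procedure together. Appendix H, B.3 opens with a different object, "AEs will be categorized according to the likelihood that they are related to the study intervention", and then returns to the wording of 8.1.2. The SAE form (Appendix F) asks for the relationship to the intervention, has a line on which a device can be specified, and offers three levels where 8.1.2 has four.

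**Treatments.** Under section 7.2 each child receives "sequential periods of both investigational treatment (nasal reservoir cannula plus nasal cannula) and standard of care treatment". Section 6.2.1 identifies the only investigational product as "investigational device (nasal reservoir cannula) treatment".

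**Procedures.** A capillary blood gas is taken at the end of each period (sections 4.2.2.1 and 4.2.2.2, Appendix A). Appendix H, B.4 states: "Expected risks to the subjects are mild discomfort due to blood draws".

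**Analysis.** Section 10.5.6 tabulates all AEs and treatment-related AEs by treatment group. It adds: "AEs will be listed and summarized by treatment group, verbatim term, severity, seriousness, and relationship to study drug". The same term appears in section 10.5.3: "Subjects who discontinued study drug prematurely or withdrew from the study will be summarized and listed".

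**The concern.** The trial is meant to inform later studies of the safety of mask plus cannula against cannula alone. For that purpose a related AE should mean one that the investigator attributes to the mask. Here the investigator answers a single question about several possible causes at once, and the analysis section reports the answer against an object that was never asked about. A sore finger from a capillary sample, nasal irritation from the prongs and carbon dioxide retention under the mask can all be rated as related, and the rating does not tell them apart.

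An analysis plan cannot fully repair this. It can rename the study drug, but it cannot split a pooled judgment after it has been recorded. Asking the investigator again later would mean retrospective attribution in an open-label trial.

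**Working it through.** The protocol gives no AE rate, so there is no figure to reproduce. The check sets the texts side by side and then uses assumed rates to show how much could be at stake.

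**1. What the rated object covers**
- *Mask:* yes, as the investigational device (6.2.1).
- *Standard cannula and oxygen:* arguably. Section 7.1 has every eligible child begin study treatment, and Group B begins on cannula alone. Section 7.2, however, distinguishes investigational treatment from standard of care.
- *Blood draws:* the term procedure is undefined but naturally includes them. Read literally, the highest causality level in 8.1.2 is met by a known effect of a procedure alone. The lowest level requires certainty that there is no relationship.

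**2. What is rated against what is tabulated**

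| Place | Object |
|---|---|
| 8.1.2 | study treatment or procedure |
| Appendix H, B.3 | study intervention, then study treatment or procedure |
| SAE form | intervention |
| 10.5.6 | treatment, and study drug |

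Nothing maps one object to another.

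**3. What can still be recovered**
Appendix A marks AE recording separately for Period 1 and Period 2, the sequence is known from randomisation, and 10.5.6 lists verbatim terms. A rate of all AEs by device in use therefore follows. If treatment group in 10.5.6 means device in use, that comparison is already planned. If it means Group A or B, each column mixes both devices, because every child receives both.

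**4. Possible size, on assumed rates**
At the maximum of 20 children there are 20 × 2 = 40 end-of-period draws.

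Let p be the share of draws recorded as a related AE. Assume a mask-caused incidence of 15% against 0% on the cannula, independent of draw events. For a per-child table of any related AE by device:
- mask: 1 − (1 − p)(1 − 0.15)
- cannula: p
- difference: 0.15(1 − p)

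| p | Mask | Cannula | Difference |
|---|---|---|---|
| 0.05 | 19.25% | 5% | 14.25 points |
| 0.25 | 36.25% | 25% | 11.25 points |

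A second illustration uses an assumed 5% mask rate (m), 5% cannula rate per hour (c), and 5% to 20% per draw (b). The mask hour is 1 − (1 − m)(1 − c)(1 − b) and the cannula hour is 1 − (1 − c)(1 − b).
- b = 5%: 14.3% against 9.8%, difference 4.5 points.
- b = 20%: 27.8% against 24.0%, difference 3.8 points.

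Pooled over both hours, the share of children with any related AE is 1 − (1 − m)(1 − c)²(1 − b)². This is 22.6% to 45.1%, or 4.5 to 9.0 of 20 children, against a mask share of 5%, or 1 of 20. So the contrast by device changes little, while the level of a pooled related row says little about the mask.

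**The case against.** The strongest reply is that most of the safety information survives. A reader might infer that no mask-related AE rate can be obtained at all. The documents do not support that: period, sequence and verbatim term give an AE rate by device in use, and a finger-prick event would be recognisable by its term. Carbon dioxide retention, the most obvious mask-specific hazard, is also measured directly in each period, by transdermal recordings every 15 minutes and an end-of-period blood gas, without any causality judgment.

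A reader might also infer that the mask-cannula difference shrinks towards zero. That needs most draws to be recorded as AEs, for which the protocol gives no basis; the samples are 0.095 mL (Appendix J) and the risk is described as minimal. It also needs a per-child table of any related AE. The only counting rule in 10.5.6 works by verbatim term, and under it a draw event does not hide a mask event in the same child, so the assumed 15 points would stay 15.

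Three further points deserve weight. The treatment-related row need not include events attributed to a procedure. The study drug wording is probably left over from a template and misleads nobody about the product. The AE page of the case report form is not at hand and might already separate the causes.

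What stands is narrower. As written, 8.1.2 and Appendix H ask for one pooled rating, nothing keeps procedure events out of the related row, and no later table can recover an attribution that was not collected.

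**Conclusion.** The point holds as a minor one. The planned tables provide no investigator-attributed, mask-specific related-AE rate, and procedure events can be counted as related. The protocol does not allow the size to be computed. Any loss in the by-device difference is the factor 1 − p, it arises only in a per-child table of any related AE, and it is under 1 point for an assumed 15-point difference when p = 0.05. The 15%, the 5% rates and every value of p are assumptions. The study drug wording by itself is clerical. The case for change rests on the low cost of collecting separate attributions while events are being recorded.

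**What to change.** - In 8.1.2, Appendix H, B.3 and the SAE form, rate each AE separately for its relation to (a) the nasal reservoir cannula, (b) the standard cannula or oxygen, and (c) study procedures such as blood draws. Use the same causality levels in all three places.
- In 10.5.6, replace study drug with investigational device; make the same wording change in 10.5.3.
- In 10.5.6, show device-related and procedure-related AEs in separate rows, tabulated by the device in use at onset, and state that this is what treatment group means there.

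The cost is two more tick boxes per AE and a revised table shell. No extra patients, visits or samples are needed.
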